5.4 Visit Schedule

Initial screening in routine clinic

Patients will normally attend a routine clinic to learn their diagnosis and treatment options. Those men identified as suitable candidates for Active Surveillance, and who appear to fulfil the inclusion criteria for the study, will be informed about the PROVENT study as an option within Active Surveillance. The clinic doctor will explain the study to the patient and a Patient Information Sheet will be given to him to take home for consideration. A follow up appointment will be arranged for him to return to confirm his treatment preference, and his initials and day (dd) of birth will be recorded on the locally held Prescreening Log.

Consent Visit

If, at the follow up appointment, the patient expresses a wish to take part in the study, the Investigator or Research Nurse will explain the aims, methods, anticipated benefits and potential hazards of the trial, ensure they have been fully understood and allow the patient the opportunity to ask questions. If the patient is still willing to take part, he will be given a pre-randomisation registration ID. This will be generated within the PROVENT application using the patient's initials and day, (DD), of birth. The consent form will be completed and signed as previously described, & the Eligibility Assessment eCRF will be completed using the pre- randomisation ID for reference.

Serum Calcium Testing

An existing serum calcium result will be acceptable if taken within 2 months prior to the Eligibility Assessment date. Alternatively, once consent has been obtained, a blood sample will be taken to confirm serum calcium is within the acceptable range for participation in the study. The result will be obtained prior to the randomisation visit and, if above the accepted range, the patient and his GP will be informed of the result and the randomisation visit cancelled.

PSA Testing

An existing PSA result will be acceptable if taken within 3 months prior to the Eligibility Assessment date. Alternatively, once consent has been obtained, a blood sample will be taken to confirm the PSA level is within the acceptable range for participation in the study. The result will be obtained prior to the randomisation visit and, if above the accepted range, the patient and his GP will be informed of the result and the randomisation visit cancelled.

Finally, an appointment will be made for the randomisation visit, and a stool specimen requested for the Helicobacter Pylori (H Pylori) test.

Helicobacter pylori testing

H pylori is a risk factor for gastric ulceration and bleeding, therefore all participants will undergo testing to rule out infection at randomisation as an additional precaution. As stated in Section 5.2 the test should not be carried out within four weeks of antibiotic treatment, or within two weeks of taking PPl's. For patients taking regular Proton Pump Inhibitors (PPIs), these must be discontinued, and an alternative treatment, such as an H2 antagonist, prescribed for the two weeks preceding the test date. Patients will be required to bring the stool specimen to their randomisation appointment. GPs will be informed of the

result and, where positive, patients will be required to visit their GP and undergo a combination of antibiotic and PPI treatment if they wish to continue in the study (See section 4.11). Participants may continue to take their study medication whilst taking the H Pylori treatment.

Randomisation Visit

Where necessary the result(s) of the serum calcium, and/or PSA tests will be assessed by a member of the PROVENT team prior to this visit to confirm eligibility. If the patient's serum calcium level is 2.65mmol/l or less, the patient may join the study. A PSA result of 15.0 ng/ml or less is required before a patient can be recruited into the trial.

If eligibility is confirmed, patients will be randomised via the online PROVENT app, and a unique study number allocated. Relevant eCRFs (Appendix 1) will be completed by the Investigator or a member of the research team, with paper based backup CRFs available in case of system failure or for additional convenience. Where paper CRFs are used, they should be kept in the investigator site file and will be reviewed as part of source data verification during site monitoring. Patients will be identified only by initials and trial number.

A digital rectal examination (DRE) will be carried out by the Investigator, clinician or a Nurse Specialist followed by the collection of a 20-35ml, first catch urine specimen for exploratory research. A 2.5ml sample will be transferred into each of the provided collection tubes as per the collection kit instructions and labelled with the unique sample identifier. These will need to be frozen locally in an ultra-low temperature freezer, (-60 to -90°C) within one hour of collection. The date and time the samples were frozen must be recorded in a separate log and sent to CCO when requested.

Residual urine will be transferred into each of the provided collection tubes and frozen locally in an ultralow temperature freezer (-60 to -90°C) until ready to be batch shipped for translational research. These translational research samples will be analysed at a later date, & may also be made available to the scientific community outside of QMUL, for ethically approved research. Where this occurs, the samples will always remain pseudo-anonymised, i.e. identified by a unique identifier.

Blood samples will be taken as directed in the Laboratory Manual for baseline serum androgens and Vitamin D3 levels, and an additional sample taken for translational research. Any routine samples not previously collected may also be taken at this time.

The stool specimen will also be collected at this visit and sent to the local laboratory to be tested for H Pylori infection.

Finally, a PROVENT prescription, and wallet cards will be issued, and an appointment arranged for three months' time in the regular Active Surveillance clinic. A **six months'** supply of study medication may then be collected from the hospital pharmacy by the patient.

Biopsy samples taken at different stages and where tumour has been confirmed, will be requested by the local site staff from the relevant pathology laboratory, and where available, sent to the Orchid Research Tissue Bank for current & future storage. Anonymised pathology report forms will also be requested for central review.

Ideally, two formalin fixed paraffin embedded (FFPE) biopsy samples with cancer confirmed should be sent. However, if this is not feasible, one biopsy block with tumour confirmation with the corresponding Heamatoxylin & Eosin stained slides, is acceptable. The samples will be used for CCP(ii) score analysis, pathology review and translational research. For the CCP(ii) score analysis, the samples will be sectioned and sent to Myriad Laboratories. The remaining biopsy material will be tissue microarrayed (please refer to the Orchid Tissue Bank SOPs; LAB005 & LAB023)

Follow-up Visits

Once randomised, participants will attend routine Active Surveillance appointments every three months (+/- 7 days wherever possible), and with the exception of the 'End of Study' visit, follow up PROVENT appointments will take place at the same time. Hence only one additional visit is required.

The literature suggests that once Aspirin's anti-platelet effect wears off, (7 to 10 days after stopping the drug), prothrombotic effects may manifest acutely within 30 days, particularly in those who either have risk factors for, or a history of cardiovascular disease. [49-52]. Therefore, the End of Study Visit will take place at 18 months plus ≥ to 30 days, to accommodate a pharmacovigilance period, when AEs & SAEs may still be reported.

Where a participant fails to stop treatment at the 18mth time point, or does not attend their 'End of Study' appointment, the LCO is responsible for checking their AE status via a telephone call at least 30 days after the date the participant has stated they stopped their IMP dose.

Follow-up CRFs will be completed at each visit (Appendix 1), and any required blood samples taken as scheduled. A further post-DRE urine sample will be collected at the 12 and 18 month visits.

Participants will be asked to return their unused medication six monthly at the 6, 12, & 18 month timepoints for compliance evaluation. Diaries will be checked at each visit, and a new diary card will be issued every three months. In addition, a PROVENT prescription will be issued six monthly, enabling a further supply of study medication to be dispensed by the pharmacy.

Prior to the 12-month appointment, arrangements will be made for a repeat MRI scan and prostate biopsy as per routine care. As previously stated in Section 4.11, patients will be advised to stop the study tablets for a week prior to their biopsy appointment, and for two days after the procedure has taken place.

Patients will continue on the study for 18 months unless their prostate cancer is found to have progressed when reclassified following prostate biopsy. Any patient whose cancer has progressed but is still deemed suitable for continued surveillance by their treating clinician may continue on the study if authorised by the Principal Investigator at that centre. Participants with cancer progression, undergoing radical therapy, must come off the trial, and an 'End of Study' eCRF must be completed. Data collected up to that point will remain part of the trial. Where a radical prostatectomy is carried out, every effort will be made to obtain pathological data and/or tissue, providing it can be acquired before the participant attends their PROVENT End of Study appointment. It is estimated that up to 30% of men will be identified to have disease progression upon disease reclassification'

. A patient whose cancer is found to have progressed before or after the 12-month biopsy will be managed as for rising serum PSA (see below).

For patients who continue on the study for the full 18 months, plus ≥30 days duration, following their Final Visit they will either revert to routine 3 monthly Active Surveillance appointments, or be offered the opportunity to enter the main PROVENT study if available at that time. In this event, it will be necessary for further consent to be obtained from the patient.

Management of rising serum PSA during the study period

Patients may experience a rising serum PSA during the 18-month study period. It is at the clinician's discretion to either recommend a 'for cause' repeat prostate biopsy, or alternatively, recommend radical therapy. However, it is recommended that an off-protocol 'for cause' prostate biopsy only be performed if the patient's PSA doubling time is less than 12 months. In addition, it is recommended but not mandated that all patients undergo repeat biopsy for a rising serum PSA rather than undergo immediate radical therapy.

Prostate biopsy

Participants will be required to stop the trial tablets for 7 days prior to prostate biopsy. If there is no sign of significant bleeding in the urine or from the rectum 48 hours after the biopsy, the tablets may be restarted. There is no requirement to stop the Vitamin D3/placebo Vitamin D3.

Repeat biopsies may occur from week 48 to week 56 depending on clinic waiting times; therefore study medication may be taken for up to four weeks more, or less, than 12 months in the weeks leading up to the routine biopsy.

Patients will undergo biopsy with prophylactic antibiotic administration as per normal procedures. This may be either a TRUS biopsy or a template biopsy and performed under local anaesthesia or general

anaesthesia using a 12 Hz ultrasound probe. The procedure will comprise a standard systematic biopsy together with targeted biopsies taken from any MRI detected abnormalities.

Biopsy cores should be sent to local laboratories separately from each region of the prostate, with no more than two cores per pot, and labelled according to the region of the prostate sampled. In patients with MRI detected prostate lesions, at least one targeted biopsy core should be directed to each lesion and placed in a separately labelled pot. Tissue taken will be processed locally as per the PROVENT Laboratory Manual.

If clinically necessary, repeat biopsy can be brought forward, or not performed, at the discretion of the Investigator. Alternatively, a patient may decide to leave the trial and undergo radical prostate cancer therapy during the 18-month study period; however the case should be presented at a multidisciplinary team meeting before an alternative management strategy is commenced. Patients who undergo radical treatment will stop trial medication at this point and not be followed up. Patients remaining on Active Surveillance but not undergoing a repeat biopsy will remain in the study for analysis as PSA dynamics over the study period will still be available.

Abnormal laboratory test results

A laboratory abnormality in one of the study specific tests, such as serum corrected calcium or H Pylori, may require the subject to undergo treatment. A value flagged, for example, as 'clinically significant' must be entered on the Adverse Event CRF. In addition, the test may need to be repeated at the Investigator's discretion. The Investigator may use his/her own judgment as to whether the abnormal finding is sufficient reason to immediately withdraw the patient from the study.

Any laboratory value that meets the definition of Serious Adverse Event must be reported as an SAE (refer to 7.1.3). In addition, the patient should be reassessed for continuation in the study and any indicated and appropriate therapies should be initiated.

5.5: Schedule of Assessment (in diagrammatic form)

	School of Medicine and Dentistry										
	Pre-	Screening	Randomisatio	3 month	6	9	12 month	15 month	18month visit	Pre 18 month	End of Study ^d
	study	& Consent	n Visit	visit	month	month	visit	visit		withdrawal	
Assessment/Action					visit	visit					
Pre-Screening log	Х										
completed	^										
Patient Information	Х										
Sheet issued	^										
Eligibility Assessment		Х									
CRF completed		^									
Informed Consent Form											
Signed		X									
3151104											
Randomisation			X								
Medical history		Х									
Height & weight			Х				Х			Xc	
Research urine samples											
for:											
Exploratory Research			X				Х		X		
Translational research			Х				х		Х		
Digital Rectal Exam (SP)			X ^a	X ^a			Χ ^a	Χ ^a	X ^a	Χ ^a	
MRI Scan	Xp						Xp			X (if scanned)	
Prostate biopsy for: Translational research tissue and CCP (ii) analysis	X _p						Х _р			X (if biopsied)	

Assessment/Action	Pre- study	Screening & Consent	Randomisatio n Visit	3 month visit	6 month visit	9 month visit	12 month visit	15 month visit	18month visit	Pre 18 month withdrawal	End of Study ^d
Helicobacter pylori test			Х								
Blood samples for:											
PSA	X p	X p		Χ ^a			Χ ^a	X ^a	X ^a	Χ ^a	
Serum calcium	X p	X b			Х		Х		Х	X ^c	
Testosterone			Х		Х		Х		Х	Xc	
LH			Х		Х		Х		Х	Xc	
FSH			Х		Х		Х		Х	Xc	
Serum Vitamin D3			Х		х		х		Х	Х	
Translational research			Х		Х				Х	Х	
Adverse Event(s)				х	Х	Х	Х	х	X ^d	Х	х
Prescription issued			x		х		Х				
Patient Diary Issued			Х	Х	х	х	х	Х			
Patient diary checked for compliance				х	Х	Х	х	х	Х	Х	

Key:

- **a** Standard practice
- **b** -Prior to appointment, or at screening if the test result is not within a valid time frame; 2 months prior to the date of the Eligibility Assessment for the serum calcium result & 3 months prior to the date of the Eligibility Assessment for the PSA result.
- **c** Where withdrawal is prior to 12month follow-up
- d Where a participant fails to stop treatment at the 18mth time point, or attend their 'End of Study' appointment, the LCO is responsible for checking their AE status via a telephone call at least 30 days after the date the participant states they have stopped their IMP dose.

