3.2 Inclusion Criteria

- 1. Male subjects aged 16 years or over with an estimated life expectancy of more than 3 years
- 2. Willing and able to provide written informed consent
- 3. Serum calcium (corrected) ≤2.65mmol/l
- 4. No previous treatment for prostate cancer (including surgery, hormone therapy, radiotherapy, cryotherapy)
- 5. All subjects must have undergone Magnetic Resonance Imaging (MRI) of the prostate with targeted biopsy of any identified lesions in addition to standard systematic biopsy.
- 6. Histologically confirmed prostate cancer following prostate biopsy including at least 10 cores of prostate tissue, in men opting for Active Surveillance as their primary cancer therapy.

Biopsies should be at least a 10-core systematic ultrasound guided prostate biopsy. For the majority of men the route of biopsy is likely to be transrectal, although the perineal route is not a contraindication to study participation. Targeted biopsies may be performed via the transrectal or perineal route. Men are eligible for the PROVENT study providing concordance exists between the location of MRI detected lesion and the location of positive biopsy core. If no concordance exists, a further prostate biopsy with lesion targeting will be required prior to randomisation, and histological analysis must fulfil study definition as a low to intermediate risk prostate cancer.

Targeted biopsies of MRI lesions must be sent in a separate pot/s from systematic biopsies and be clearly labelled. A minimum of two targeted biopsies per MRI detected lesion is required.

At 12 months, all men will be required to undergo repeat prostate biopsy. Again, the route of biopsy, transrectal or perineal, is not mandated. Patients must have systematic and targeted biopsies at the 12-month point using the same methods as described at study entry.

All patients included in the study should be enrolled in an Active Surveillance management programme for prostate cancer. Patients may be included if they have Gleason 6 or 7, (Gleason 3+3 or 3+4), organ confined disease, with a PSA of 15.0 ng/ml or less, and have a clinical and radiological stage of less than T3. The largest cancer core length should be less than 10mm.

Patients must have undergone a multi-parametric MRI deemed assessable by the study radiologist, and any lesions seen must have undergone targeted biopsy (transrectal or transperineal) within 12 months of study registration.

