3.4 Criteria for treatment discontinuation and early withdrawal

Treatment discontinuation

One year following study entry, patients will undergo disease reclassification to identify cancers that have progressed over the 12-month period. Disease reclassification will include repeat MRI of the prostate, together with repeat systematic and targeted prostate biopsy. Any patient whose cancer has progressed as defined in section 1.1, may continue on the study, providing they;

- are still deemed suitable for continued surveillance by their treating clinician
- do not undergo radical therapy &
- are authorised to do so by the Principal Investigator at that centre.

The reason for continuing on Active surveillance should be documented on the eCRF.

Patients undergoing radical therapy will discontinue study medication and an End of Study eCRF will be completed. No more study follow-up appointments will take place. The decision to proceed with radical therapy will be at the clinician's and patient's discretion. Unless explicitly requested in writing, by the

participant, data collected up to the 'End of Study' date will remain part of the trial. This will usually include the 12mth samples & eCRFs, as in most cases, these will have already been collected by the time the results of the disease reclassification are available.

Where a radical prostatectomy is carried out, every effort will be made to obtain pathological data and/or tissue, providing it can be acquired before the participant attends their PROVENT End of Study appointment. It is estimated that up to 30% of men will be identified to have disease progression upon disease reclassification.

Where progression is found and/or the decision is made to undergo radical therapy after 12 months but before 18 months, the participant will be required to leave the trial. An End of Study form must be completed, \geq 30 days after the participant took their last dose of IMP, for post treatment pharmacovigilance. Samples that would normally have been obtained at the 18 month follow-up appointment, will be collected wherever possible.

Early withdrawal

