8.2 Secondary Endpoint Efficacy Analysis

The secondary endpoints include response to treatment as determined by serial multi-parametric magnetic resonance imaging (MRI) of the prostate, biochemical disease progression, histological disease progression together with the evaluation of markers of disease progression.

- Disease progression on MRI will be defined as the development of a MRI detected lesion of 0.2 cc or greater and scoring 4/5 on PIRADS criteria, where no MRI lesion was identified on screening MRI, a 33% increase in the volume of previously identified lesions or an upgrading of MRI stage of disease to ≥3.
- . The outcome will be described as a proportion of the study cohort.

Biochemical disease progression will be defined as a 50% increase in serum PSA at 12 months from baseline. Again this will be described as a proportion of the study cohort.

Histological disease progression will be defined as an increase in Gleason score following repeat prostate biopsy from:

Gleason 6 to Gleason score 7 or higher Gleason 3+4 (score 7) to 4 + 3 (score 7) or Gleason 4+3 (score 7) to a higher score

Or a 50% increase in maximum cancer core length (MCCL)

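### Section 5.4 lets the 12-month biopsy take one targeted core per MRI lesion where section 3.2 requires two, so known lesions may be sampled less at follow-up than at entry

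*Protocol*

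**What the plan says.** Section 3.2 (Inclusion Criteria) describes the biopsy at entry and also looks ahead to month 12. For systematic sampling it says "Biopsies should be at least a 10-core systematic ultrasound guided prostate biopsy". For MRI lesions it says "A minimum of two targeted biopsies per MRI detected lesion is required". For follow-up it says "Patients must have systematic and targeted biopsies at the 12-month point using the same methods as described at study entry".

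Section 5.4 (Visit Schedule, under Prostate biopsy) describes how the repeat biopsy is done: "Repeat biopsies may occur from week 48 to week 56 depending on clinic waiting times". It continues: "The procedure will comprise a standard systematic biopsy together with targeted biopsies taken from any MRI detected abnormalities". Then, for men with MRI-detected lesions: "at least one targeted biopsy core should be directed to each lesion and placed in a separately labelled pot". It does not refer back to 3.2.

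These cores feed the histological progression endpoint in sections 2.2 and 8.2, which is met by a defined Gleason increase or by a 50% rise in maximum cancer core length (MCCL). Section 3.4 gives the only anticipated rate: "It is estimated that up to 30% of men will be identified to have disease progression upon disease reclassification".

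**The concern.** The endpoint is a change between two biopsies, so the two should sample a given lesion with the same intensity. Section 5.4 allows half the entry minimum at the second one. It is also the section that staff arranging the repeat biopsy are likely to consult; the two-core rule sits under the inclusion criteria.

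The direction of any error is known. A Gleason upgrade can be missed with fewer cores but not created. MCCL is a maximum over cores, so dropping one lowers it or leaves it as it was. If some sites take one core and others two, the progression proportion would be understated by an amount that differs across the sites, of which there are up to seven.

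Two uses of the result are exposed. Section 1.5 ties the numbers for a definitive trial to the disease progression rate seen here. The 12-month reclassification in section 3.4 also bears on whether a man stays on surveillance and on study medication. An analysis plan cannot repair this, because it cannot recover a core that was never taken.

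**Working it through.** **Comparing the two sections**

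| | Section 3.2 | Section 5.4 |
|---|---|---|
| Applies to | Entry, and month 12 through the same-methods sentence | Repeat biopsy, weeks 48–56 |
| Minimum targeted cores per lesion | 2 | 1 |
| Strength of wording | Required / must | Should |

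The same-methods sentence can be read in two ways. If it carries the core count forward, 5.4 contradicts 3.2. If it covers only route and technique, the protocol sets a lower minimum at follow-up than at entry. Either way the minimum for a known lesion is not held constant.

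The point concerns men whose lesion was already targeted at entry. Men with no MRI lesion are unaffected. A lesion first seen at 12 months has no earlier targeted sample to be compared with.

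**Illustrating the size**

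The protocol states no figure that could be reproduced here, and gives no detection rates. The following inputs are assumptions:

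- *p*, the chance that one targeted core finds an upgrade: 0.3 to 0.7
- *ρ*, the correlation between two targeted cores in the same lesion: 0 to 0.6
- *s*, the chance that the systematic cores find the upgrade, independently of the targeted cores: 0 (ignored), then 0.3 to 0.7

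Detection with one targeted core: D1 = 1 − (1 − p)(1 − s).

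Detection with two: D2 = 1 − [(1 − p)² + ρp(1 − p)](1 − s).

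Worked example, p = 0.3, ρ = 0, s = 0.3: D1 = 1 − 0.7 × 0.7 = 0.51; D2 = 1 − 0.49 × 0.7 = 0.657; ratio 0.51 / 0.657 = 0.776.

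Ratio D1/D2 over the grid:

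| s | ρ | p = 0.3 | p = 0.5 | p = 0.7 |
|---|---|---|---|---|
| 0 | 0 | 0.59 | 0.67 | 0.77 |
| 0 | 0.6 | 0.78 | 0.83 | 0.89 |
| 0.3 | 0 | 0.78 | 0.79 | 0.84 |
| 0.3 | 0.6 | 0.90 | 0.90 | 0.93 |
| 0.5 | 0 | 0.86 | 0.86 | 0.89 |
| 0.5 | 0.6 | 0.94 | 0.94 | 0.95 |
| 0.7 | 0 | 0.93 | 0.92 | 0.94 |
| 0.7 | 0.6 | 0.97 | 0.97 | 0.97 |

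On targeted cores alone, one core finds 59–89% of what two find. With systematic cores counted (s from 0.3 to 0.7), it finds 78–97% (0.776 to 0.973).

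**Ceiling on the endpoint**

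Suppose the full 30% from section 3.4 were Gleason upgrades in men with known lesions, all 102 men were biopsied, and every site took one core.

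- Rate: 30% × 0.776 = 23.3%; 30% × 0.973 = 29.2%.
- Men: 102 × 0.30 = 30.6 expected; 30.6 × 0.776 = 23.7; 30.6 × 0.973 = 29.8. The shortfall is about 1 to 7 men.
- Sampling error on 30% of 102: 1.96 × √(0.3 × 0.7 / 102) = 0.089, about ±9 points.

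No figure is offered for the MCCL component. It depends on true growth and on the spread of core lengths, and the protocol gives neither.

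**The case against.** The best defence is that the stricter 12-month rule is already written down, and in firmer language. Section 3.2 says what patients must have and what is required; 5.4 says what should be done, in a paragraph mainly about pots and labelling. Two cores satisfy both sections, and a one-core site breaches an explicit requirement. On this view the defect is a missing cross-reference.

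That has force as to severity. Thinner sampling is allowed by 5.4 read alone, but it is not certain to happen, and the protocol does not say which section sites follow. It does not remove the conflict, because the section describing the procedure states the lower number without pointing to the higher one.

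A second objection is that nothing decisive moves. The primary endpoint is recruitment, and progress to the main trial rests on recruitment, adverse effects and funding. That is right, and it limits the point to a secondary endpoint. Section 1.5 does, however, give the progression rate a role in planning the later trial.

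A third objection is that the numbers are largely assumed and the ceiling is stretched. That also stands. The 30% is itself an upper estimate, and progression under section 1.1 also includes MRI, PSA, MCCL and metastatic criteria. Section 5.4 also lets an investigator omit the repeat biopsy. The calculation shows direction and an outer limit and is not a forecast. That the effect lies within sampling error does not excuse it: sampling error falls either way, whereas this error can only lower the rate.

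**Conclusion.** The two minimums conflict and the protocol does not resolve them. A site working to 5.4 may sample a known lesion with one core after at least two at entry, and the histological progression proportion would then be understated or unchanged, never overstated.

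The effect is modest. Under the assumed ranges, one core retains 78–97% of the upgrades that two would detect once systematic cores are counted. The extreme case turns 30% into 23–29%, less than the sampling error on 102 men. The true effect depends on how many sites take one core, which the document does not show.

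The recruitment endpoint is unaffected. Allocation to active or placebo is blinded, so there is no reason for core counts to differ by arm. The point should be corrected because the direction of error is known and the correction is very cheap; it does not threaten the trial's main purpose.

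**What to change.** In section 5.4, replace the clause setting a one-core minimum with: *a minimum of two targeted cores must be taken from each MRI-detected lesion, as at study entry (section 3.2)*. The instruction on separate labelling can stay, since 5.4 allows up to two cores per pot. Writing *pot or pots* would also cover a site that takes three or more cores from one lesion.

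The cost is one sentence. Sites already working to 3.2 change nothing. Sites taking one core add one per lesion at a biopsy that is already scheduled, with a small added bleeding risk. Nothing is asked beyond what 3.2 already requires.

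### The adverse-event check at least 30 days after the last dose has no stated interval for men who stop for radical therapy before month 12, and the follow-up rules for them conflict

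*Protocol*

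**What the plan says.** Protocol section 5.4 (Follow-up Visits) gives the reason for the check. Once aspirin's antiplatelet effect has worn off, a clotting risk may appear, and the times given are "7 to 10 days after stopping the drug), prothrombotic effects may manifest acutely within 30 days". For that reason "the End of Study Visit will take place at 18 months plus" at least 30 days. If a man is still taking treatment at 18 months, or misses that visit, the site must telephone him at least 30 days after his stop date. Key d of section 5.5 repeats this.

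Section 3.4 carries the interval to one group of early leavers. When progression or a decision for radical therapy comes after month 12 and before month 18, the End of Study form waits until at least 30 days after the last dose.

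For radical therapy in general, section 3.4 stops the drug, asks for an End of Study eCRF and adds: "No more study follow-up appointments will take place". Section 5.4 says "Participants with cancer progression, undergoing radical therapy, must come off the trial", again with an undated End of Study eCRF. Under Prostate biopsy it allows a man to leave and "undergo radical prostate cancer therapy during the 18-month study period", and then states: "Patients who undergo radical treatment will stop trial medication at this point and not be followed up".

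Section 5.12 keeps withdrawn men under three-monthly clinic follow-up unless they have withdrawn permission in writing. Section 3.4 discontinues men whose dosing is interrupted for a cumulative total above 60 days between visits, with an End of Study eCRF and no further appointments.

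**The concern.** The hazard named in section 5.4 runs from the last dose, whenever that falls. The month 12 to 18 rule in section 3.4 accepts this. Nothing in the protocol suggests the hazard is absent for a man who stops at month 5 or month 10.

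Such men are foreseen. With a rising PSA at any time in the study, the clinician may recommend a for-cause biopsy "or alternatively, recommend radical therapy". The repeat biopsy may be brought forward, and even the routine one can precede month 12: "Repeat biopsies may occur from week 48 to week 56 depending on clinic waiting times".

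A site following section 5.4 as written can close such a man's record inside the period the protocol itself treats as risky. A site following section 5.12 would see him again. What may be lost is post-treatment adverse-event information and some protection for the participant. The 24-hour serious-event reporting clock in section 7.4.1 does not compensate, because it starts only when the team becomes aware of an event.

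**Working it through.** No figure in the protocol needs reproducing. The check sets the exit rules side by side.

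| How the man stops | Stated check after last dose | Where |
|---|---|---|
| Completes 18 months | Visit at 18 months plus at least 30 days; telephone fallback | 5.4; 5.5 key d |
| Progression or radical therapy, months 12 to 18 | End of Study form at least 30 days after last dose | 3.4 |
| Radical therapy before month 12 | No interval; appointments end, no follow-up | 3.4; 5.4 |
| More than 60 days' interruption | No interval; End of Study eCRF, no further appointments | 3.4 |
| Withdrawn, follow-up continues | Three-monthly clinic visits; 30-day timing not explicit | 5.12 |
| Declines all further contact | None possible | 3.4 |

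**Does another provision cover radical therapy before month 12?**

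- *Adverse-event mark under pre-18-month withdrawal (section 5.5, Appendix 1).* It requires a check but gives no timing. It could be completed on the day of stopping, before the risk period opens.
- *End of Study appointment.* Sections 3.4, 5.4 and 5.6 mention one for men having prostatectomy. Section 5.4 dates that visit only at 18 months plus at least 30 days.
- *Telephone fallback.* It is triggered by missing the End of Study appointment. Whether a man told he has no more follow-up appointments has such an appointment to miss is unclear.
- *Section 5.12.* It would keep him in three-monthly follow-up, but section 5.4 says the opposite.

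**Conflict over the whole period.** The no-follow-up sentence in section 5.4 is not limited to the first 12 months. Applied at month 14, it contradicts the month 12 to 18 rule in section 3.4.

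**Men with more than 60 days' interruption.** The total is cumulative within a three-month interval. A man who stopped outright more than 60 days ago is past day 30. One who dosed intermittently may have taken a tablet just before the visit, so only some of this group are exposed to the gap.

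**Scale.** Section 3.1 gives six arms of 17.

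- All men: 6 × 17 = 102. On active aspirin: 4 × 17 = 68. Share: 68 / 102 = 0.67.
- The protocol gives no rate for radical therapy before month 12. Assuming 1% to 5%: 0.01 × 102 = 1.0 to 0.05 × 102 = 5.1 men. On active aspirin: 0.01 × 68 = 0.7 to 0.05 × 68 = 3.4.
- For contrast, up to 30% are expected to progress at reclassification: 0.30 × 102 = 30.6. Most of these should fall under the month 12 to 18 rule, which already has the interval.

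**The case against.** The strongest reply is that an End of Study contact is intended for everyone. Section 5.4 distinguishes the End of Study visit from the routine follow-up appointments, so ending follow-up can mean only that the three-monthly visits stop. The telephone fallback is worded as alternatives and timed from the actual stop date, not from month 18. Read generously, it reaches early leavers. This has force. It makes the fault one of unclear and conflicting wording, not of a check plainly abolished. It does not settle the matter, because the only date given for the visit is tied to 18 months and section 5.4 tells sites the opposite.

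Two stronger readings are tempting and should not be drawn.

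- A reader might infer that no contact at all is required on leaving. The untimed adverse-event mark under pre-18-month withdrawal and the references to an End of Study appointment contradict that.
- A reader might count men who leave with no further visits as a second gap. Section 3.4 first offers them follow-up by eCRF, clinic or telephone. Only those who refuse it have no visits, and respecting refusal is not a design fault.

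It is also fair that placebo aspirin carries no withdrawal hazard, that current daily aspirin users are excluded, and that section 5.4 places the risk mainly in men with cardiovascular risk factors or history. The early routine biopsy adds little, since section 3.4 expects month-12 data usually to be in hand before the results arrive. All this limits the size of the problem.

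How many risk days an untimed check would miss should not be computed. If the 30 days run from stopping, the window closes at day 30. If they run from loss of effect, it closes at day 7 + 30 = 37 to 10 + 30 = 40. The wording allows either.

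**Conclusion.** The point holds as a minor safety fault in a stated rule. The protocol ties the check to the last dose and gives its reason, yet states no interval for men who stop for radical therapy before month 12. One sentence in section 5.4 points sites away from any later contact and conflicts with sections 3.4 and 5.12. Some men discontinued for interrupted dosing share the gap. Men who decline all contact do not.

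The size cannot be derived from the protocol. It is probably a few men at most, about two thirds of them on active aspirin if early leaving does not depend on arm. The 1% to 5% range is an assumption made only to show scale. Recruitment, the primary endpoint, is unaffected.

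**What to change.** In sections 3.4 and 5.4 and in key d of section 5.5, require the existing clinic or telephone adverse-event check at least 30 days after the last dose for every man who permanently stops study medication, whatever the reason or time, unless he refuses contact. Let any visit on or after day 30 count. Complete the End of Study eCRF only after that check, as section 3.4 already does for months 12 to 18.

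In section 5.4, replace the no-follow-up clause with wording such as *no further study visits other than this check*. Reconcile it with the radical-therapy and interruption rules in section 3.4 and with section 5.12.

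The cost is a wording amendment, about one call per early leaver under a procedure sites already have, and a delay of about 30 days in closing each such record.
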